Concerns have been raised about cardiovascular safety of rosiglitazone, based on the initial (2007) and the updated (2010) meta-analyses of clinical trials by Nissen and Wolski^{3,4} and a Medicare-based study by Graham et al.⁵ These studies provided evidence of an increased risk of several cardiovascular outcomes in users of rosiglitazone compared with users of other oral antidiabetic medications or placebo. The postmarketing RECORD trial, ordered by a regulator and sponsored by the manufacturer, GlaxoSmithKlein, published in 2010,⁶ showed no overall effect of rosiglitazone on the primary outcome of cardiovascular morbidity and mortality. The trial, however, has been criticized for methodological flaws, including open-label design, considerable selection bias, and possible irregularities in case adjudication.⁷

In response to the safety concerns raised in 2007, EMA emphasised the need for providers "to adhere to the restrictions for use in patients with cardiac disease", but advised patients "not to stop treatment with rosiglitazone and to discuss the medication with their doctor at their next regular visit."⁸ In 2007, EMA concluded "that the benefits of [...] rosiglitazone [...] in the treatment of type 2 diabetes continue to outweigh their risks."⁹ In January 2008, EMA added contraindications for rosiglitazone to its label.¹⁰ The Food and Drug Administration in the United States also issued a boxed warning. The proportion of rosiglitazone prescriptions among all diabetic medications except insulin dropped in the US from around 11% in March 2007 to 6% in July 2007 and to less than 3% in 2009.¹¹

Following the two 2010 publications,^{4,5} the EMA suspended rosiglitazone-containing drugs from the European markets, on 23 September 2010.¹² On 3 December 2010, the European Commission (EC) issued a suspension decision, noting that risk minimisation in form of label warnings and restricted use has not been clearly effective. The scientific discussion accompanying the suspension decision noted that persons with indications for rosiglitazone may have an a-priori higher risk of cardiovascular morbidity. Still, based on all available evidence, the EC concluded that rosiglitazone does not provide unique therapeutic benefits that outweigh the risks of cardiovascular outcomes.¹³

The present study was commissioned by the European Medicines Agency (EMA), following the suspension of rosiglitazone preparations in the European Union. EMA wishes to retrospectively examine the impact of risk minimisation actions in the European Union (such as warnings, scientific publications, and regulatory decisions) on utilization of rosiglitazone and on the condition of rosiglitazone-using patients with type 2 diabetes (the target population).

2 Specific aims

The specific aims of this study are as follows:

- To describe trends in patterns of utilisation of rosiglitazone-containing preparations over time, in particular, in response to external events, such as scientific and media publications, EMA's press releases, or EMA's regulatory decisions aimed at risk minimisation;
- To examine the extent of use of rosiglitazone-containing preparations in persons with potential contraindications;
- To examine the extent of use of rosiglitazone-containing preparations in persons outside the primary indication (off-label use);
- To examine risk of acute drug reactions among patients who switch from alternative antidiabetic therapies to rosiglitazone preparations or vice versa;
- To examine glycaemic control and other objective parameters of disease among patients who switch from alternative antidiabetic therapies to rosiglitazone preparations or vice versa.

3 Methods

3.1 *Setting and study population*

This study will be conducted in Denmark and in the United Kingdom (UK).

In Denmark, the source population includes residents of the country's North and the Central regions, with combined population of about 1.8 million, or approximately 33% of the population. Denmark is a welfare state, with universal, tax-funded access to all medical services, including reimbursement for prescribed medicine. Many medical services rendered in Denmark have been routinely and prospectively recorded, on patient level, for the past several decades in population registries; data linked from these registries will be used in the present study.¹⁴

In the UK, the study will be conducted based on data from the General Practice Research Database (GPRD). The GPRD is an ongoing longitudinal database that collects data from over 350 general practices in the UK since 1987. The UK provides a unique medical environment to create a computerized medical data resource for medical epidemiological research for two main reasons: a) the primary health care system comprehensively covers the UK population; b) the information on all relevant medical care is located in the offices of the general practitioners (GPs), who function as "gatekeepers" for hospital and specialist referrals in the UK health system. The GPRD contains information on more than 6 million patients, of whom 3.5 million are currently registered, and a

cumulative follow-up time of more than 40 million person-years. It covers 6% of the UK population; this sample is representative with respect to age, gender and race/ethnicity distribution.

The study population will include, in both countries, diabetic patients treated with oral glucose lowering drugs between 1 January 2000 and 1 January 2011. This period covers the time from the approval of rosiglitazone for use in the European Union, in July 2000, until the decision by the European Medicines Agency to suspend the drug, on 23 September 2010. The study period also includes a pre-approval and a post-suspension periods to allow examination of drug utilization patterns in response to these events.

3.2 Study design

The study objectives will be addressed using cohort design based on individual-level data linkage. The design will take advantage of existing records that will have accumulated over decades, and is therefore a retrospective cohort design. Measurement and recording of exposure (prescription for oral glucose lowering medication) precedes measurement and recording of the study outcomes (e.g., acute reactions, changes in laboratory parameters).

Because of concerns over the cardiovascular safety of rosiglitazone, it would be unethical to use an experimental study to address the study objectives. Furthermore, while experimental studies answer the question about drug efficacy and safety in carefully selected and closely observed patient populations, observational studies are better suited for evaluation of the drugs' 'real-world' utilization and safety.¹⁵ A cohort study based on linkage of population-based routine records has the advantage of avoiding selection bias that could ensue in a cohort study with routine data collection if patients self-selected to participate or to drop out of the study.

3.3 Exposure definition and measurement

To identify users of oral glucose lowering medications, including rosiglitazone, we will use the Aarhus University Prescription Database (AUPD)¹⁶ in Denmark and the General Practice Research Database (GPRD) in the UK.¹⁷ The AUPD tracks prescription dispensations, while the GPRD records prescriptions issued by physicians. Antidiabetic medications are available by prescription only in both countries.

We will identify patients with *two or more* prescriptions for oral glucose lowering drugs redeemed (in Denmark) or issued (in UK) between 1 January 2000 and 1 January 2011. Because dispensed prescriptions contain personal identifiers, we will be able to determine the number of unique users of each oral glucose lowering drug or their combinations. Currently, AUPD contains data on approximately 2,400, while GPRD has data on approximately 20,000 users of rosiglitazone preparations.

Based on recorded prescription dates, we will examine the patterns of oral glucose lowering drug use during the study period. A person will be considered a switcher once they have received two or more prescriptions for a new therapy. Users will be classified into several categories (not all drug combinations listed below may exist in the actual data):

- Those who receive rosiglitazone monotherapy as the first oral glucose lowering drug;

- Those who use oral glucose lowering drugs other than rosiglitazone (classified by type of drug);
- Those who switch from oral glucose lowering drugs other than rosiglitazone to rosiglitazone;
- Those who switch from rosiglitazone to an alternative oral glucose lowering drug. This group may include people who received alternative oral glucose lowering drugs before rosiglitazone use;
- Those in whom rosiglitazone is added to a prior alternative therapy;
- Those in whom an alternative oral glucose lowering drugs is added to rosiglitazone therapy.

List of medications, with codes used to identify them, appears in Appendix 1.

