3.4.3 Acute drug reactions

Both acute and pre-existing events will be identified in the Danish National Registry of Patients and in the Registry of Causes of Death in Denmark and in the GPRD's Event file, in the UK.

Acute drug reactions will be defined as new (first-onset) events occurring 45 days after the date of the switch to or from a rosiglitazone preparation. We will use prior hospitalization records to screen out prevalent/prior events and conditions. The exact distribution of events that may represent a potential acute drug reaction is unknown until data analysis. We will rank all recorded new events in the order of seriousness and potential of representing an acute drug reaction. Since cardiovascular side effects are a major safety concern for rosiglitazone, as a minimum, we will examine the following events:

- All-cause mortality;
- Cardiovascular mortality;
- Acute myocardial infarction;
- Cerebrovascular accident/ischemic stroke
- Pulmonary embolism;
- Deep vein thrombosis.

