3.6 Analysis plan

3.6.1 Drug utilization patterns

Based on the dates of rosiglitazone marketing, publications, and regulatory decisions, the following four broad periods can be identified, in which drug utilization patterns will be examined, starting with 1 July 2000, when rosiglitazone was introduced to the EU market:

- | | |
|----------|---|
| Period 1 | 1 July 2000 to 23 May 2007 (meta-analysis & by EMA's press release) |
| Period 2 | 24 May 2007 to 24 January 2008 (EMA adds contra-indications) |
| Period 3 | 25 January 2008 to 22 September 2010 (EMA suspends rosiglitazone) |
| Period 4 | 23 September 2010 until data closing date. |

We will evaluate prescribing patterns within these periods and according to calendar month by several methods. First, we will calculate (separately in Denmark and in the UK):

- The number of persons receiving prescriptions for rosiglitazone in each time period, overall and per month during the time period;
- The number of prescriptions for rosiglitazone in each time period, overall and per month during the time period;
- The number of persons receiving a prescription for any specific antidiabetic medication in each time period, overall and per month during the time period;

- The proportion of persons receiving a prescription for any specific antidiabetic medication who received a prescription for rosiglitazone in each time period.

We will describe switching patterns in several ways within each database. First we will determine the proportion of patients on anti-diabetic therapies other than rosiglitazone who switched to rosiglitazone in each of the 4 time periods. We will also describe the proportion of people, by time period, who switched from rosiglitazone to another anti-diabetic medication or who discontinued use of any anti-diabetic medication. Proportions of patients discontinuing rosiglitazone preparations will be determined among those who originally switched to rosiglitazone and among those for whom the rosiglitazone-containing product was the first-ever anti-diabetic prescription. Switching will be defined as 1) stopping all rosiglitazone prescriptions and starting a different anti-diabetic medication, 2) stopping all anti-diabetic medications or 3) adding new anti-diabetic therapies to the current rosiglitazone therapy (concomitant therapies). A person will be considered a switcher once they have received at least 2 prescriptions for a new therapy.

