3.6.3 Acute drug reactions

For patient-level endpoints, baseline will be defined as the recorded date of medication switch/addition (as reflected by a new dispensation/issue); date of the first-time prescription dispensation/issue (in first-time users) or 1 January 2000 (in prevalent users).

We will examine the number of potential drug reactions occurring within 45 days of baseline and calculate the 45-day cumulative incidence of acute drug reactions, overall and diagnosis-specific (if the data set is large enough); We will estimate risk ratios for the acute drug reactions identified using regression, while adjusting for confounding.

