3.6.4 Glycaemic control and other biochemical disease parameters

We will compare recorded plasma glucose concentration, HbA1c values, and other objective disease parameters before and after the baseline. Because the date of dispensation/issue does not precisely indicate the exact date of patient medication switch, we do not know the precise day that the patient starts the new medication), it will be important to explore different time windows after the recorded dispensation/issue date. We will compare measurements at various time points before and after the baseline. The latest measurement before the baseline will be assumed to indicate the baseline value for the analysis. The follow-up time after baseline is expected to vary depending on the date of available laboratory testing. We will conduct analyses examining 1, 3, and 6-month post-baseline changes in laboratory parameters.

Furthermore, we will examine the potential role of secular trends – scientific or media publications and EMA warnings – by controlling in the analysis for time elapsed from an event that could potentially trigger medication switch and the time of actual switch (approximated by the date of the new prescription). We propose that recency of potential triggering events may be an indirect indicator of patient's underlying risk of potential adverse events as perceived by patients themselves or their providers.

4 Quality assurance, feasibility and reporting

This study will be carried out by scientists employed at academic institutions. The study in Denmark will be conducted by the study coordinator, the Department of Clinical Epidemiology (DCE), Aarhus University, Denmark. The study in the UK will be conducted by the Boston Collaborative Drug Surveillance Program (BCDSP), which is an independent research unit affiliated with Boston University, USA. The study was commissioned to the Department of Clinical Epidemiology by the European Medicines Agency. EMA is the sole sponsor of the study. Because

EMA required that data from at least two EU Member States be included in this evaluation, DCE subcontracted BCDSP to conduct the analyses in the United Kingdom.

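### Switchers are defined by a second prescription of the new drug but followed from the new dispensation, so the 45-day incidence of death, and of reactions that end treatment, is biased downward

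*Protocol*

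**What the plan says.** Three rules in the protocol bear on this point.

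- **Who is a switcher.** Section 3.3: "A person will be considered a switcher once they have received two or more prescriptions for a new therapy". Section 3.6.1 says the same: "A person will be considered a switcher once they have received at least 2 prescriptions for a new therapy".
- **When the clock starts.** Section 3.6.3, for switches and additions: "baseline will be defined as the recorded date of medication switch/addition (as reflected by a new dispensation/issue"). For the other groups it is the "date of the first-time prescription dispensation/issue (in first-time users) or 1 January 2000 (in prevalent users"). Section 3.6.4, which uses the same baseline, treats the dispensation date as a stand-in for the start of the new drug because "we do not know the precise day that the patient starts the new medication".
- **What is counted.** Section 3.4.3 defines acute reactions as "new (first-onset) events occurring 45 days after the date of the switch to or from a rosiglitazone preparation". Section 3.6.3 says: "We will examine the number of potential drug reactions occurring within 45 days of baseline". Of the six events listed as a minimum, two are mortality endpoints (all-cause and cardiovascular). Section 3.6.3 promises a 45-day cumulative incidence and adjusted risk ratios.

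A fourth rule governs entry to the study population. Section 3.3 requires two or more "prescriptions for oral glucose lowering drugs redeemed (in Denmark) or issued (in UK) between 1 January 2000 and 1 January 2011".

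No section says how a patient who dies or stops after one prescription of the new drug is handled.

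**The concern.** Membership of the switcher group depends on something that happens after follow-up has begun. Between the first and second prescription of the new drug, a person who will be counted as a switcher cannot die. That stretch is immortal time, and it falls where an acute reaction to the change of drug would be looked for.

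At stake is the fourth specific aim, the risk of acute reactions after switching to or from rosiglitazone. Early deaths would disappear from the count without trace, and an analyst following the text would report a mortality incidence that is too low. The protocol gives no warning of this. Section 3.2 describes exposure as recorded before outcome, whereas here exposure status may be settled only after the outcome window has closed. Section 4 expects little selection bias, on the ground that data collection is routine, and does not consider selection created by the definitions themselves.

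This cannot be left to a later analysis plan, because the protocol itself fixes both the classification rule and the baseline.

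**Working it through.** The protocol gives no expected event count or risk for this endpoint, so there is no figure to reproduce. The check shows how large the loss could be.

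**Inputs from the protocol:** window W = 45 days (3.4.3, 3.6.3); at least two prescriptions of the new therapy (3.3, 3.6.1); baseline at the new dispensation (3.6.3), read as the first.

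**Assumptions, none given in the protocol:** the second prescription comes at day *d*, the same for everyone; the hazard of death *h* is constant; the true 45-day risk of death is 0.2% to 1%.

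**Deaths.** A switcher must be alive at day *d*. With m = min(d, 45):

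- share of 45-day deaths removed = [1 − exp(−h·m)] / [1 − exp(−45h)], close to m/45;
- observed risk among counted switchers = 1 − exp(−h·(45 − m)).

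Worked case, true risk 1%, d = 28: h = −ln(0.99)/45 = 0.000223 per day. Observed risk = 1 − exp(−17 × 0.000223) = 0.38%. Share removed = [1 − exp(−28 × 0.000223)]/0.01 = 62%. A simulation of 4 million patients gave a true risk of 1.00% and an observed risk of 0.38%.

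| Second prescription at day | Deaths removed | Observed/true risk |
|---|---|---|
| 14 | 31% | 0.69 |
| 28 | 62% | 0.38 |
| 30 | 67% | 0.33 |
| 45 or later | 100% | 0 |

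These figures barely change between true risks of 0.2% and 1%.

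**Non-fatal events.** An event is lost only if it comes before the second prescription and the patient then stops. With q the share who stop, the loss is about q·m/45. At d = 28 it is 0% for q = 0, 16% for q = 0.25, 31% for q = 0.5 and 62% for q = 1.

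**If the switch is dated at the second prescription.** The immortal time goes, but days 0 to *d* after the change fall before baseline. At d = 28 that is 28 of the first 45 days; at d = 45 or more it is all of them.

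**The other groups.** A first-time user has baseline at the first prescription and needs a second to enter, so survival to day *d* is guaranteed, as for a switcher. A prevalent user has baseline on 1 January 2000, which need not be a prescription date, and needs two prescriptions from then on. If the first comes between day 0 and day *d*, the second comes between *d* and 2*d*. At d = 28 the guaranteed survival is 28 to 56 days, against 28 for a switcher.

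**The case against.** The strongest reply is that the two-prescription requirement applies to everyone, so the comparison may be less distorted than the incidence. That stands. A reader might infer that the risk ratios are biased towards making switching look safe, especially against prevalent users followed from 1 January 2000. The protocol does not support this. Prevalent users must also survive to a second prescription after baseline, possibly a later one than switchers need, which would push the ratio the other way. Section 3.6.3 names no comparator, and switches run both to and from rosiglitazone. Bias may partly cancel or reverse.

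Other stronger readings also fail:

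- That all early reactions are removed by definition. This is strictly true of deaths only. A patient who has an infarction and later receives a second prescription stays a switcher, and the event counts.
- That switcher mortality is zero by construction. This needs every second prescription to come at day 45 or later, which the protocol does not show.
- That the entry rule adds further immortal time for switchers. It asks for two prescriptions of any oral glucose-lowering drug, so a switcher with one earlier prescription in the study period already qualifies at the first new one.
- That dating the switch at the second prescription misses the acute period altogether. With a 28-day interval, days 28 to 45 are still seen.

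It can also be said that section 3.6.3 does not state in so many words that baseline is the first new prescription. That is correct; it is the natural reading alongside section 3.6.4. The other reading does not rescue the plan, since it leaves the first refill interval unobserved.

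**Conclusion.** Wrong as written. Taken together, the switcher rule and the baseline exclude every death between the first and second prescription of the new drug, and every non-fatal reaction after which no second prescription follows. The 45-day cumulative incidence in switchers is biased downward whatever the comparator. For deaths, the loss runs from about a third with a 14-day interval to all of them at 45 days or more. Those sizes rest on a constant hazard and one common refill interval, both assumed. With varied intervals the loss would be a mixture of the tabulated values, and a hazard concentrated soon after the change would make it larger for any interval under 45 days.

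The direction and size of bias in the risk ratios depend on the comparator and the refill intervals, and cannot be settled from the protocol. If intervals are 45 days or longer in every compared group, no 45-day death is observed in any of them and the mortality risk ratio cannot be estimated.

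**What to change.** For the acute-reaction analysis in section 3.6.3 only:

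1. Assign every compared group (switchers, additions, first-time users and prevalent users) using only information available at baseline.
2. Define a switch or addition by the first prescription of the new drug, and start follow-up on that date.
3. Require no later prescription in any group. Lifting the rule for switchers and first-time users but not for prevalent users would create a new imbalance. Prevalent users then have to be identified from prescriptions before 1 January 2000. Section 3.1 dates GPRD data collection from 1987; the start of the Danish prescription data is not stated and should be confirmed.
4. Align the wording of sections 3.3, 3.4.3, 3.6.1 and 3.6.3 accordingly.

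Keep the two-prescription rule in sections 3.3 and 3.6.1 for the descriptive utilisation tables. There it also needs reconciling with section 3.6.1's own list of switch types, which includes patients who stop all antidiabetic treatment. They can have no prescription for a new therapy, so the rule cannot apply to them, and their switch date needs its own definition.

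The cost is protocol wording and a changed query on existing records. The downside is slight dilution from single prescriptions that were never taken.

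### Sections 3.3 and 3.6.1 disagree on whether adding a drug to rosiglitazone is a switch; if the two are kept apart, a non-fatal event that ends rosiglitazone can move a patient from the addition group to the switch group

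*Protocol*

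**What the plan says.** Section 3.3 classifies users from the whole prescription record: "Based on recorded prescription dates, we will examine the patterns of oral glucose lowering drug use during the study period". Two of its categories concern patients already on rosiglitazone who receive another drug: "Those who switch from rosiglitazone to an alternative oral glucose lowering drug" and, separately, "Those in whom an alternative oral glucose lowering drugs is added to rosiglitazone therapy". It also sets a threshold: "A person will be considered a switcher once they have received two or more prescriptions for a new therapy".

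Section 3.6.1 defines switching in three limbs. The first is "stopping all rosiglitazone prescriptions and starting a different anti-diabetic medication". The third is "adding new anti-diabetic therapies to the current rosiglitazone therapy (concomitant therapies". No gap length, grace period or date of decision is attached to stopping.

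Section 3.6.3 starts the clock at the new drug: "baseline will be defined as the recorded date of medication switch/addition (as reflected by a new dispensation/issue". It then says "We will examine the number of potential drug reactions occurring within 45 days of baseline", and plans cumulative incidences and adjusted risk ratios. It names no reference group and does not say whether switch and addition are analysed together or apart.

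**The concern.** In prescription data, stopping a drug shows up as the absence of later prescriptions. On the day the new drug is issued, a patient who will leave rosiglitazone and one who will continue it usually look alike. The split between them is settled by prescriptions inside or beyond the 45-day risk window.

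The outcome can influence that split. Acute myocardial infarction is an acute outcome in section 3.4.3, and a history of it is on the contraindication list in section 3.4.1. Suppose a drug is added on day 0, the patient has a non-fatal infarction on day 20, and rosiglitazone is not prescribed again. The record then reads as a switch on day 0 followed by an infarction. Without the infarction the same patient is an adder.

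The fourth specific aim is the acute risk of switching to or from rosiglitazone. If exposure is partly defined by the outcome, leaving rosiglitazone can look harmful and adding to it can look safe when neither has an effect. Covariate adjustment does not repair this. It also contradicts section 3.2, which says that exposure is recorded before outcomes.

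**Working it through.** **1. The definitions side by side.**

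| Section | Drug added, rosiglitazone continued | Drug started, rosiglitazone stopped |
|---|---|---|
| 3.3 | own category | own category |
| 3.6.1 | switch (third limb) | switch (first limb) |
| 3.6.3 | one baseline date for switch or addition; grouping not stated | same |

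Under the 3.6.1 scheme, moving a patient from adder to switcher changes nothing, because both are switchers. Under the 3.3 scheme it changes both group risks.

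**2. When the label is known.** It is known on day 0 if rosiglitazone is prescribed the same day, or if the new product is a fixed combination containing rosiglitazone (these have their own codes in Appendix 1). It is known before the event if a rosiglitazone refill falls between baseline and the event. Otherwise it depends on what follows the event.

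**3. Size for non-fatal events.** The protocol has no figure to reproduce. All inputs here are assumptions: true 45-day risk r = 0.3% in both groups; A = 1 or 2 additions per switch; s = share of adders with an event who are reclassified because the event ends rosiglitazone.

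- Switch-from risk = (r + A·r·s) / (1 + A·r·s)
- Addition risk = r(1 − s) / (1 − r·s)

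Example, A = 2 and s = 0.5: switch-from risk = (0.003 + 0.003) / 1.003 = 0.598%, which is 1.99 times the truth. Addition risk = 0.0015 / 0.9985 = 0.150%.

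| A | s | Switch-from risk | Times truth | Addition risk | Ratio of the two |
|---|---|---|---|---|---|
| 1 | 0.1 | 0.330% | 1.10 | 0.270% | 1.22 |
| 1 | 0.3 | 0.390% | 1.30 | 0.210% | 1.85 |
| 1 | 0.5 | 0.449% | 1.50 | 0.150% | 2.99 |
| 2 | 0.1 | 0.360% | 1.20 | 0.270% | 1.33 |
| 2 | 0.3 | 0.479% | 1.60 | 0.210% | 2.28 |
| 2 | 0.5 | 0.598% | 1.99 | 0.150% | 3.98 |

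**4. Role of the refill interval.** A simulation made the refill interval explicit. It assumed a true risk of 1.0% in both groups, equal numbers intended as switchers and adders, and the two-prescription rule in force. A stop was read as no rosiglitazone prescription after baseline.

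| Event ends rosiglitazone in | Refill interval | Switch-from risk | Addition risk |
|---|---|---|---|
| 25% | 28 days | 1.08% | 0.92% |
| 50% | 28 days | 1.17% | 0.84% |
| 50% | 56 days | 1.33% | 0.71% |
| 50% | 90 days | 1.35% | 0.62% |

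If a stop is instead read as rosiglitazone ending inside the window, 50% stopping gives about 1.5% against 0.5% at every interval. With no stopping after events, or with the groups pooled, the risk returns to about 1.0%.

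**5. Deaths.** If the second prescription of the new drug falls on day 28, only deaths after day 28 can be counted: (45 − 28)/45 = 0.38 of them. With all events fatal, the simulated risks were 0.38% in switchers and 0.39% in adders, so the inflation cancels. With 56- or 90-day refills no death within 45 days is counted in either group. If a stop is read as rosiglitazone ending inside the window, the deaths still counted with 28-day refills all fall in the switch group (0.76% against 0). No general direction can be given for deaths.

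**The case against.** The strongest reply is that the only explicit definition of switching, in section 3.6.1, already includes additions to rosiglitazone, and section 3.6.3 uses a single baseline for both. On that reading the bias does not arise. This is correct as far as it goes. But section 3.3 keeps the groups apart, the 3.6.1 definition sits under drug utilisation, and section 3.6.3 does not choose between them.

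A reader might infer that the plan will compare switchers with adders and so produce a false ratio of up to about 4. The documents do not state that contrast, and no reference group is named. The supportable measure is the inflation of the switch-from risk itself.

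A reader might also infer that every listed outcome ends rosiglitazone. Of the six minimum outcomes in section 3.4.3, only myocardial infarction is on the list in section 3.4.1; stroke, pulmonary embolism and deep vein thrombosis are not. Section 3.6.2 treats ischaemic heart disease and peripheral vascular disease as contraindications added in 2008. The stopping probability may therefore differ by outcome and period, and may be small for some.

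A gap rule or a reference group could stand in an analysis plan that is not shown. That stands as a limit on certainty. However, the protocol's own analysis section already fixes the switch definition, the baseline and the window, and these are what conflict. Section 4 acknowledges uncertainty in the timing of a switch, but that is a different matter from outcome-dependent grouping.

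**Conclusion.** The point holds in this form: sections 3.3 and 3.6.1 conflict, section 3.6.3 does not resolve the conflict, and under the section 3.3 grouping a non-fatal event can determine the exposure label. The direction for non-fatal events is clear: switch-from risk goes up and addition risk goes down. The size is not. It is about 1.1 to 2.0 times for the switch-from risk if 10% to 50% of adders with an event are reclassified and there are one or two additions per switch. Short refill intervals push it towards the lower end, because more labels are settled before the event. None of these inputs comes from the documents.

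It would go too far to say that the plan is biased whichever way it is read, since pooling removes the problem for non-fatal events. It would also go too far to extend the direction to deaths, since the two-prescription rule drops early deaths from both groups and can cancel the inflation. The sponsor should settle the definition before the acute-reaction analysis is run.

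**What to change.** In section 3.6.3, define the main acute-reaction exposure only from information up to the baseline date: *new antidiabetic drug started while on rosiglitazone*, with switch and addition combined, and likewise *rosiglitazone started while on another drug*. State the look-back that counts as current use. Make sections 3.3, 3.6.1 and 3.6.3 consistent with this.

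The requirement for a second prescription of the new drug also uses information from after baseline. If it is kept for this analysis, combining the groups cures the bias for non-fatal events but not the loss of early deaths.

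If switch and addition are to be shown apart, classify all patients at one fixed landmark after baseline and count only events after it, with the length of the later window stated. Labelling only patients with an early event as undetermined is not a substitute. It removes events but not the event-free patients at the same point, and so biases both split risks downwards. The look-ahead split can stay in the utilisation tables of section 3.6.1.

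The cost is wording and a new derivation of groups from data already held. The main estimate will not separate switch from addition, and the landmark analysis will omit events before the landmark.
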